### 3.12 How and when will consent be obtained from participants and any third parties?

See *National Statement Chapter 2.2 and Chapter 3.1 Element 3*. Templates for [consent forms](#) should be modified to suit the nature of the project.

Those who indicate an interest in participating in the study will be emailed a plain language information sheet and consent form. Additionally, they will be provided an electronic link to the REDCap patient information sheet and Consent Form. The consent form will only be accessed through the patient information sheet to ensure this information is read prior to electronic consent. Participants may choose whether to use the hard copy form or the electronic clinic provided.

Participants will be given time to read the form and discuss with family and/or support persons before responding with their interest. Those who do not respond will be contacted no more than twice by email or telephone after which they will be deemed not interested in study participation.

The POTS-LCS investigators will be available to review the informed consent form with potential participants upon request and address any questions or concerns prior to obtaining written informed consent for POTS-LCS participation.

Consent for future use of blood samples drawn during this study for POTS related research will be included on the Patient information and consent form. The investigators will also address any future questions or concerns of POTS-LCS participants.

Signed consent forms will be kept on record and a note in the patient's medical file (if a patient of the CHRD) will be made indicating their desire to be involved in the study. Institutional ethics and study approval will be informed by policies of the National Health and Medical Research Council of Australia and will be secured from the University of Adelaide, Human Research Ethics Committee before commencement of the trial, in accordance with humane experimentation requirements.

### 3.13 For participants not fluent in English or who have difficulty understanding English, what arrangements will be made to ensure comprehension of the research information?

N/A

### 3.14 Will the researcher(s) be taking photographs or recordings of participants using audio tape, film/video, or other electronic medium? If so, how will these be used?

This information should be provided to participants in the participant information sheet and the consent form.

No such data will be used for the study

**3.15 In reference to Question 2.5, indicate all research activities in the study and where applicable outline the approximate time commitment required of participants.**

Consult the [definitions of research methods](#) for guidance on selecting the method(s) applicable to the project:

Research method/activity		Participant time	Research method/activity		Participant time
Action research			Interventional		
Biospecimen analysis			Interview		
Body organs, tissues or fluids		24hr urine collection	Observational		75 minutes
Clinical Trial			Phlebotomy (Blood sampling)		10 minutes
Data linkage			Survey		30 min at leisure
Drugs or isotopes If this is selected, a Drugs to be Administered Form is to be completed.			Textual analysis (including medical records, academic records, personal documents)		
Epidemiological			Use of data sets		Oz POTS
Ethnographic			Other		
Focus group					

**3.16 Provide a description of each of the activities selected above in terms of what the participant will experience from taking part in the research:**

Provide a summary of the focus of any research activities e.g. topics of the survey, interviews etc. and the format they will be undertaken e.g. face to face, online etc. If there are multiple methods, outline if participants are being asked to do one or all of the activities. Attach copies of surveys, interview or focus group schedules, questions and topics to be covered to the application. All attachments should be clearly labelled with appropriate headings and referred to within the body of the application.

**Before study testing day:**

In addition, all study participants will be sent a link to a health questionnaire and QoL surveys as listed below. These can be done at leisure and without time restriction to reduce the effects of inconvenience and survey fatigue.

1. Holter Monitor: All patients will undergo 24 hour ambulatory ECG, at home (adhesive electrodes placed on the skin and attached to a recording device). This measure will be used to determine heart rate variability; which is a measure of baseline autonomic tone. It will also help to exclude other alternative cardiac arrhythmias.
2. Echocardiogram requires the subject to undertake an ultrasound of the heart previous to the day of testing at the subject's convenience. This test is important for determining other secondary causes of symptoms due to structural cardiac changes. It requires a non-invasive ultra-sound of the heart and generally takes 15 minutes to complete. To determine associations of neuroendocrine function with changes to orthostatic filling volumes and cardiac measurements. Echocardiogram will be undertaken in the semi-fowler position and then in passive leg raise (45 degree) position after 90 seconds.
3. Demographic survey and Medical Health History including alcohol consumption, tobacco use. Past medical history, medications and allergies will be completed by the two symptomatic cohorts.

Controls will complete a health history and demographic survey to confirm absence of exclusion medical conditions and medications when attending for assessment.

4. Rand SF-36: 36 item short form survey which is commonly utilised to measure self-reported quality of life measures in adult patients.
5. EQ-5D/5L: Is a short survey utilised and validated to describe and value health across 5 domains.
6. COMPASS-31: 31 question composite autonomic scale which is utilised widely for use in autonomic research and practice. It addresses the domains of: orthostatic intolerance, vasomotor, secretomotor, gastrointestinal, bladder and pupillomotor function.
7. Fatigue Severity Score: A 9 item questionnaire that reports how fatigue interferes with certain activities and rates the severity of fatigue.
8. 5 Point hypermobility screen: Five questions related to hypermobility. A score  $>2/5$  suggests hypermobility (sens 85%, spec 90%)
9. Orthostatic Hypotension Questionnaire: A validated tool used to determine the burden and severity of orthostatic hypotension. It has two components: a 6-item symptom assessment scale and a 4 item activity scale.
10. Hospital Anxiety Depression Scale: 14 item scale with 7 items relating to anxiety and 7 to depression. A cut off score of 8 in either domain has been widely validated as a reliable indicator of anxiety or depression.

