**2.5 Research methodology:**

Describe how the study will be undertaken and explain what interactions will occur between researchers and participants. Include a description of the research methodology and how this will achieve the research aims. For example, you could include a justification of why the sample size/sampling method will yield valid and reliable results. Where appropriate, please refer back to the aims described in 2.1 when describing the methodological approach.

We plan to enrol 218 participants for this study (n= 150 with LCS, n=34 with POTS, n = 34 healthy matched controls). Subjects who meet the inclusion and none of the exclusion criteria and who provide informed consent, will be invited to attend in person to facilitate physical examination including autonomic testing, blood draw and associated investigations (see table below). The comprehensive nature of this exercise will allow subjects to complete various tools/questionnaires at their leisure via online portal links to a secure REDCap database, to reduce the impact of fatigue on the accuracy of findings.

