**Subject preparation:**

48 hr before examination the following will be discontinued

- Anticholinergics
- Sympathomimetics ( $\alpha$  and  $\beta$  agonists)
- Mineralcorticoids (Fludrocortisone)

24hr before examination the following will be discontinued

- Alcohol
- Salt tablets
- Caffeine
- Beta Blockers (propranolol, metoprolol), Ivabradine, Calcium channel blockers

[figure not shown]
8 hrs before testing

- Fast from food
- Drink only water 'to thirst' and abstain from fluid 'loading'

On the morning of testing

- No wearing of compression wear
- No abdominal binders
- No support stockings

Figure 1: Project Schema

As participants in this study are excluded from having other significant cardiac impairments or significant medical conditions, it is unlikely that drug cessation will cause any detriment other than the discomfort and inconvenience of poorly controlled orthostatic intolerance. Participants will be encouraged to discuss cessation of medications with their regular doctor. In addition, senior clinician researchers will identify those in the screening process who may have increased risk if medications are ceased. If it is decided that individuals are unable to cease the above listed medications for the prescribed time, then those participants will not be able to participate in the study. This is the case because biomarker and autonomic testing outcomes would not be deemed meaningful in the setting of artificial control of heart rate and fluid status.

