#### Discomfort and Inconvenience

The PICF will clearly highlight the potential discomfort and inconvenience that may be involved in undertaking the autonomic testing, blood test and health related questionnaires. This ensures clear disclosure and may help to prepare participants for the expected experiences.

Cessation of medications that control heart rate and expand fluid volume will inevitably result in return of unpleasant orthostatic symptoms associated with POTS/LCS. These symptoms are generally not considered dangerous but will impede on functionality and can be severe for some individuals. This has been clearly articulated in the PIS which states:

*“Some participants will be required to stop medications such as those that control their heart rate before the study day. This is so the researchers can detect differences in how your heart reacts to different tests such as the deep breathing test. Stopping these medications is likely to allow some of your symptoms such as dizziness and fast heart rate, return. This is likely to be unpleasant for you and may take some time to recover once you restart your normal medication.”*

Autonomic testing may illicit feelings of dizziness and general ‘unwellness’, particularly in those with POTS. For this reason, experienced clinicians will be in attendance at all participant testing sessions. First aid kits, comfortable, tiltable chairs, vital sign monitoring and fresh drinking water will be available for all participants. Any detrimental reactions to testing (such as fainting during blood draw) will be recorded and followed up with appropriate medical assessment by clinician/researchers. The PICF will recommend that participants are accompanied to testing by a support person in case of adverse effects of testing.

QoL surveys may be completed online through a secure link given to participants. This decreases the testing burden by allowing participants to respond at their leisure. This will reduce the associated inconvenience and will enhance completion and accuracy of outcomes. Contacts for psychological support will be detailed on the PICF should health related survey’s raise issues of concern for participants

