## **Health Questionnaire**

### **English version for Australia**

Under each heading, please tick the ONE box that best describes your health TODAY.

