## FATIGUE SEVERITY SCALE (FSS)

Date \_\_\_\_\_ Name \_\_\_\_\_

Please circle the number between 1 and 7 which you feel best fits the following statements. This refers to your usual way of life within the last week. 1 indicates “strongly disagree” and 7 indicates “strongly agree.”

Read and circle a number.	Strongly Disagree	→	Strongly Agree
1. My motivation is lower when I am fatigued.	1	2	3 4 5 6 7
2. Exercise brings on my fatigue.	1	2	3 4 5 6 7
3. I am easily fatigued.	1	2	3 4 5 6 7
4. Fatigue interferes with my physical functioning.	1	2	3 4 5 6 7
5. Fatigue causes frequent problems for me.	1	2	3 4 5 6 7
6. My fatigue prevents sustained physical functioning.	1	2	3 4 5 6 7
7. Fatigue interferes with carrying out certain duties and responsibilities.	1	2	3 4 5 6 7
8. Fatigue is among my most disabling symptoms.	1	2	3 4 5 6 7
9. Fatigue interferes with my work, family, or social life.	1	2	3 4 5 6 7

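### Self-report scales may be completed during the 24–48 h drug stop, so a medicated participant's EQ-5D can record either usual or off-drug health

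*Protocol*

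**What the plan says.** Protocol section 3.16 places the questionnaires under the heading "Before study testing day" and states: "These can be done at leisure and without time restriction to reduce the effects of inconvenience and survey fatigue". Section 2.5 lets participants "complete various tools/questionnaires at their leisure via online portal links to a secure REDCap database", and section 4.2 adds: "QoL surveys may be completed online through a secure link given to participants". None of the three gives a completion window relative to the drug stop, and none says that completion date or drug status at completion is recorded.

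Section 2.5 (Subject preparation) has two lists of items to stop. One begins "48 hr before examination the following will be discontinued" and covers anticholinergics, sympathomimetics and mineralocorticoids. The other applies at 24 hours and includes salt tablets, beta blockers, ivabradine and calcium channel blockers. On the consequence, section 4.2 says: "Cessation of medications that control heart rate and expand fluid volume will inevitably result in return of unpleasant orthostatic symptoms associated with POTS/LCS". Section 4.1 likewise expects function to decline while medication is stopped.

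The attached EQ-5D form instructs: "please tick the ONE box that best describes your health TODAY"; its 0–100 scale also asks about the same day. The Fatigue Severity Scale (FSS) says: "This refers to your usual way of life within the last week". Both parts of the Orthostatic Hypotension Questionnaire (OHQ) also look back one week.

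**The concern.** The open period for the questionnaires contains the drug stop. A treated participant who fills in EQ-5D a week before the visit reports health on usual treatment. The same person filling it in the day before the visit may report health with treatment withdrawn for the study. Both answers are correct replies to the form, and the protocol does not say which is wanted.

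Secondary objective 3 (section 2.1) compares quality of life and symptom scores in LCS with and without POTS, in POTS, and in healthy controls. The ambiguity is not shared equally. POTS participants are existing patients who have received treatment (section 3.1), while the control flyer asks for people on no regular medicine other than the contraceptive pill. A score lowered by study preparation could be read as disease impact, and the mix of on-drug and off-drug answers adds variance within the medicated groups.

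**Working it through.** The plan gives no figure for this point, so there is none to reproduce. The check sets the completion rule, the drug stop and each form's recall period side by side.

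**Overlap.** Questionnaires: any time before the test day. Drug stop: the last 24 or 48 hours before the examination. The second lies wholly inside the first.

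**Largest share of the recall period that can fall in the stop.** Formula: days off drug ÷ recall days, for a form completed at the very end of the stop.

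| Scale | Recall (attached form) | 24 h stop | 48 h stop |
|---|---|---|---|
| EQ-5D | same day | up to 100% | up to 100% |
| FSS, OHQ | 7 days | 1/7 = 14% | 2/7 = 29% |
| SF-36, four-week items | 28 days | 1/28 = 4% | 2/28 = 7% |
| COMPASS-31, past-year items | 365 days | 1/365 = 0.3% | 2/365 = 0.5% |

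For a form completed before the stop, the share is 0% on every scale.

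These are upper limits. Assume a 9 am visit and completion at 8 pm the evening before, 13 hours earlier. Time off drug is then 24 − 13 = 11 h or 48 − 13 = 35 h. For FSS and OHQ that gives 11/168 = 7% to 35/168 = 21%; for the four-week SF-36 items, 11/672 = 2% to 35/672 = 5%. The FSS also asks about usual life and the OHQ symptom part about an average, which dilutes a short change further. The HADS form is not attached, so its recall period cannot be checked.

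**Score shift.** Formula: share medicated × share completing during the stop × fall in score. The documents give none of the three inputs. As an illustration only, assume EQ-5D 0–100 scale SD 20, 80% of POTS and 20% of LCS-without-POTS participants on a listed drug, equal true on-treatment means, and 34 against 135 participants (150 less the 10% with POTS assumed in section 3.3).

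- If 50% complete during the stop and the score falls 10 points: POTS shift 0.8 × 0.5 × 10 = 4; comparator shift 0.2 × 0.5 × 10 = 1; net contrast 4 − 1 = 3 points.
- If 20% complete then and the fall is 5 points: 0.8 × 0.2 × 5 = 0.8; 0.2 × 0.2 × 5 = 0.2; net 0.6 points.
- If 50% complete then and the fall is 20 points: 8 − 2 = 6 points.

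Simulated two-sided Welch tests at a nominal 5% (5,000 runs per setting) rejected in 12.3%, 4.9% and 28.8% of runs respectively. With 20% completing then and a 10-point fall the figure was 6.0%.

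**The case against.** The strongest reply is that the effect is small and confined mainly to one instrument, in a secondary objective. Most of that stands. It would be wrong to infer that every scale records drug withdrawal: the recall shares above show only a partial effect on FSS and OHQ and little on SF-36 and COMPASS-31. It would also be wrong to take 12% or 29% as the expected false-positive rate. Those figures rest entirely on assumed inputs, and the mildest setting shows no inflation at all. Having half the participants complete the forms in the last day or two is an extreme assumption for an open link.

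A second reply is that the wording in section 3.16 concerns survey fatigue and may mean only that no single form is timed. That is possible, but it still leaves no completion window, and the section heading still admits the days of the drug stop.

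Third, the information sheet and the schema figure are not available here and might carry an instruction. That cannot be excluded, but it would not change the open timing in the protocol text.

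Fourth, off-drug scores may be what is wanted: cognitive testing, also under objective 3, is done on the test day with drugs stopped. The protocol does not say whether impact means health on or off treatment, so it cannot be claimed that only on-drug scores are valid. But section 2.5 justifies the drug stop by the biomarker and autonomic tests, not by self-report, and either aim would need a stated window. Open timing gives a mixture.

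Finally, a sensitivity analysis could be left to the analysis plan. It works only if completion date and drug status are collected, and that has to be settled before the forms go out.

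**Conclusion.** The point holds for EQ-5D. As written, section 3.16 lets a medicated participant's score reflect either usual health or health with treatment withdrawn, while controls recruited as taking no regular medicine are unaffected. This can bias and add noise to the EQ-5D comparisons in secondary objective 3. FSS and OHQ are affected in part, by at most 14% to 29% of the recall week and less when completed the evening before.

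The direction, worse scores off drug, comes from sections 4.1 and 4.2. The size cannot be computed: under the stated assumptions the net contrast ranges from 0.6 to 6 points on the 0–100 scale, and none of those assumptions comes from the documents. The primary prevalence objective and the physiological tests are not touched. This is an inexpensive improvement to data collection and does not invalidate objective 3.

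**What to change.** In section 3.16, with matching wording in 2.5 and 4.2, replace the open timing by a request that all cohorts complete the scales before the first listed drug is stopped, which means at least 48 hours before the visit. Participants can still do so at home and in as many sittings as they need, so the aim of limiting burden is kept.

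Leave the link open for late forms, since closing it would turn late answers into missing ones, possibly from the most fatigued participants. Record on each form the completion date and whether any listed drug had already been stopped. Keep all forms from participants who stopped no drug. Run a sensitivity analysis of EQ-5D, and of FSS and OHQ, without forms completed during the drug stop.

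The cost is one or two sentences, two recorded items, a slightly shorter window for participants, and a few forms set aside in the sensitivity analysis. The drug-stopping rule is not changed.

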### Study testing day:

The following testing protocol will take approximately 60-90 minutes to complete. A schematic representation of the protocol can be seen (Figure 1: above)

Non-invasive measurements of continuous arterial pressure and heart rate will be obtained using finger photoplethysmography (non-invasive blood pressure testing; NIBP) for 5 minutes before testing (rest) and then during each reflex test. This involves application of a small cuff to either of the 2nd to 5th digits of

one hand. The cuff is inflated to allow measurement of finger arterial blood pressure. This technique is well validated in a variety of clinical and experimental conditions and is similar to our prior protocol. Description of each test can be found in section 3.16

Testing variables	Cohort 1	Cohort 2	Cohort 3
Demographic Survey	X	X	X
Medical health history	X	X	X
Medications use	X	X	X
Physical examination	X	X	X
Health Related QoL			
- SF-36 [36-Item Short Form Survey]	X	X	X
- EQ-5D [5 level EQ score]	X	X	X
- COMPASS-31 [composite autonomic symptom scale]	X	X	X
- FSS [fatigue severity score]	X	X	X
- 5 Point hypermobility screen	X	X	X
- OHQ [orthostatic hypotension questionnaire]	X	X	X
Autonomic testing			
- Standing test, deep breathing, Valsava manoeuvre	X	X	X
- Sudomotor function (SUDOSCAN)	X	X	X
- 24-hour Holter monitoring	X	X	X
- Echocardiogram with Passive Leg Raise	X	X	X
Blood tests:			
- Complete Blood Panel and Electrolytes, CRP, ESR,	X	X	X
# TNF- $\alpha$ , IL-6, IL-1 $\beta$ , IL-10, IL-21, INF $\gamma$ , INF $\alpha/\beta$ , CD30,	X	X	X
# $\alpha$ 1 adrenergic, Beta-1 adrenergic, M1 and M4 muscarinic	X	X	X
cholinergic receptor Ab;			
# Aldosterone, Potassium, Renin activity, copeptin level;	X	X	X
# Plasma Histamine, heparin, chromogranin A	X	X	X
24 hr Urinary volume and osmolarity	X	X	X
Cognitive and psychological testing			
- CANTAB (Cambridge neuropsychological test automated battery)	X	X	X
- HADS (hospital anxiety and depression scale)	X	X	X

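### The 24-hour Holter, and probably the leg-raise echocardiogram, are recorded before the full drug stop that the protocol treats as necessary for meaningful autonomic results

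*Protocol*

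**What the plan says.** Protocol 2.5, Subject preparation, gives one set of drug stops. The first list opens with "48 hr before examination the following will be discontinued" and covers anticholinergics, sympathomimetics and fludrocortisone. A 24-hour list follows, which includes beta blockers, ivabradine, calcium channel blockers and salt tablets. The instructions then run on to an 8-hour fast and to "On the morning of testing". People who cannot stop are not enrolled, on the ground that "biomarker and autonomic testing outcomes would not be deemed meaningful in the setting of artificial control of heart rate and fluid status".

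The table in 2.5 lists "24-hour Holter monitoring" and "Echocardiogram with Passive Leg Raise" in its autonomic testing block, for all three cohorts.

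Section 3.16 puts both under the heading for activities before the testing day. The Holter is worn at home for 24 hours: "This measure will be used to determine heart rate variability; which is a measure of baseline autonomic tone". It also serves to exclude arrhythmia. For the scan, "Echocardiogram requires the subject to undertake an ultrasound of the heart previous to the day of testing", at a time that suits the participant. The scan has two purposes: to look for structural causes of symptoms, and to relate neuroendocrine function to filling volumes with a passive leg raise. Blood is drawn on the testing day (3.16, Study Day Testing, item 6). Neither recording is given a drug stop.

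**The concern.** The protocol sets a standard for autonomic outcomes and then schedules two of the measures it lists as autonomic testing where that standard is not met.

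Drug exposure is likely to differ between cohorts. Section 4.1 expects some participants to be on drugs that control heart rate, while the healthy-volunteer flyer asks for people on no regular medication other than the contraceptive pill. A difference between patients and controls in heart rate variability or leg-raise filling could then come partly from treatment. Fludrocortisone and salt tablets matter for the scan in particular, because they bear on fluid status. The planned association between filling volumes and neuroendocrine markers, which bears on secondary objective 2, would also pair a scan in one drug state with blood drawn in another.

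**Working it through.** The plan gives no figure to reproduce here; the check is a timeline. Let T be the start of testing on the study day. From 2.5, drugs on the 24-h list stop at T − 24 h and drugs on the 48-h list at T − 48 h. Hours into the stop at a recording made h hours before T are 24 − h and 48 − h. A negative value means that the drug has not yet been stopped.

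**Holter, most favourable case.** It runs from T − 24 h to T.
- 24-h list: from 24 − 24 = 0 h to 24 − 0 = 24 h, a mean of 12 h.
- 48-h list: from 48 − 24 = 24 h to 48 h.

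The full stop is reached only as the recording ends.

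**Holter ending at midnight before the test day** (assumption: T between 08:00 and 12:00). It starts at T − 32 h to T − 36 h, so 32 − 24 = 8 h to 36 − 24 = 12 h fall before the 24-h stop begins. That is 8/24 = 33% to 12/24 = 50% of the recording. An earlier Holter has more.

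**Echocardiogram at 17:00 on the eve** (same assumption on T). This is T − 15 h to T − 19 h.
- 24-h list: 24 − 15 = 9 h down to 24 − 19 = 5 h.
- 48-h list: 48 − 15 = 33 h down to 48 − 19 = 29 h.

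A scan more than 48 h before T precedes every stop.

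**What a full stop for the Holter would need.** If the recording ends at T, the 24-h list would have to stop by T − 48 h and the 48-h list by T − 72 h. The protocol does not ask for this.

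**Precision of an untreated subset**, relevant to the fix (two-sided 5% two-sample t test, 80% power, 34 controls). The share of treated patients is not stated, so 25%, 50% and 75% are assumed.

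| POTS patients in the comparison | Detectable difference |
|---|---|
| 34 (all) | 0.69 SD |
| 26 (34 × 0.75 = 25.5) | 0.74 SD |
| 17 (34 × 0.50) | 0.85 SD |
| 9 (34 × 0.25 = 8.5) | 1.08 SD |

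These figures concern POTS patients against controls only. At the planning prevalence of 10%, about 150 × 0.10 = 15 Long COVID participants would have POTS, so an untreated subset of that group would be thinner still.

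**The case against.** The strongest counter-argument is that the word examination in 2.5 may cover more than the test day. The opening of 2.5 speaks of an in-person examination that includes the investigations in the table, and both recordings are in that table. The adverts mention two visits for cardiovascular testing. The project schema (Figure 1), which might settle the timing, is not visible in the copy reviewed, and that is no fault of the plan. A stop before an earlier visit is therefore possible for the echocardiogram. It would not help a 24-hour recording worn at home. The run of instructions up to the morning of testing, and the information-sheet excerpt in 4.2 that ties stopping to the study day, both point to the test day. A reader might take that excerpt as proof that participants are told of one stop only. It is an excerpt and does not say so.

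A second argument is that autonomic testing in 2.5 may mean only the attended session, and that both recordings also serve as screening, which justifies doing them early. If so, the inconsistency with the protocol's own standard falls away, but the difference in drug state remains.

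A third is that medication use is already collected in all cohorts and that adjustment belongs in an analysis plan. This is partly right. But knowing who takes a drug does not show how long before a recording it was last taken, and no part of the protocol asks for that.

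**Conclusion.** On the plain reading, heart rate variability from the Holter is not measured at the full stop. The same is likely, with less certainty, for leg-raise filling. Cohort comparisons of both, and the association of filling volumes with study-day blood results, may partly reflect drugs.

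Three stronger conclusions are tempting and not supported:
- That the recordings are made on full treatment. One made on the eve falls partly inside the stop; only a scan more than 48 h earlier is certain to precede all stops.
- That the bias has a known direction or size. The share of treated participants and their drugs are not stated, and a drug effect could create a difference or hide one.
- That the prevalence of POTS is affected. The standing test takes place on the study day, after the stops.

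Neither measure is named in the objectives in 2.1, so this concerns secondary profiling only. The times of day and the treated shares used in the calculations are assumptions. The change is worth making because it is cheap and the missing timing would be hard to recover later.

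**What to change.** Record the date and time of the last dose of each listed drug, counting salt tablets, when the Holter is fitted and when the echocardiogram is done; for the Holter, also note doses taken during the recording. State in 2.5 that these two measures are not taken at the full stop. Report their cohort comparisons, and the association of filling volumes with blood results, with drug state accounted for. Add a sensitivity analysis in participants taking none of the listed drugs.

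The cost is one added data item and one sentence, with no extra time off treatment. The untreated subset is less precise and may contain milder patients, so it should not be the main comparison.

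Keep the structural echocardiogram and the arrhythmia check before drugs are stopped, since 2.5 and 4.1 rely on serious heart disease having been excluded. Do not move the leg-raise scan to the test day only at sites that have echocardiography. Section 2.6 offers the university rooms to controls alone, so a partial move could tie fasting and drug state to cohort. Move it for all cohorts or not at all.
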